10.5 SAFETY ANALYSES

All safety endpoints will be summarized using the safety population.

Adverse Events

The number of subjects reporting: adverse events, serious adverse events, adverse device effects, serious adverse device effects, and unanticipated serious device effects will be summarized. In addition, for each adverse event, the following will be summarized: severity, the relationship to investigational device use, outcome and duration of the resolved adverse events and the duration of the adverse events at trial discontinuation.

Device deficiencies

The number of device deficiencies and the number of patients reporting a device deficiency will be summarized as well as a summary of device deficiencies with the potential to cause SADE.

Additional summaries of safety endpoints, if applicable, will be described in the SAP.

10.6 INTERIM ANALYSES

A formal interim analysis will be conducted once 50% of the planned subjects reach the 6-month follow-up visit to assess how the relative performance of the two treatments differ over time.

CONFIDENTIAL AND PROPRIETARY

Study Protocol	Smith-Nephew
A Prospective, Multi-center, Randomized Controlled	Number:
Study to Evaluate the Safety and Efficacy of ARCR	REGENETEN.2020.01
augmented with REGENETEN™ Bioinductive Implant	Version: 2.0, 08 Dec
System in Full-thickness Tears (large or massive) Repair	2021
versus ARCR alone	Page: 75 of 134

11. SAMPLE SIZE JUSTIFICATION

Using a group sequential design, a formal interim analysis will be conducted once 50% of the planned 260 subjects reach the 6-month follow-up at which point a sample size re-estimation will be performed along with options considered to terminate early for efficacy or futility or to increase sample size for power. Further details will be specified within the SAP.

The initial RCT power analysis is based on a Lan-DeMets (O'Brien-Fleming) spending function with hypothesized retear incidence of 15% for REGENETEN and 30% for conventional ARCR with 80% power and 5% significance level.

The sample size of 260 RCT (130 ARCR augmented with REGENETEN and 130 ARCR alone) is based on a primary hypothesis of 50% reduction in retear rates.

12. ADVERSE EVENTS AND DEVICE DEFICIENCIES

12.1 DEFINITIONS

The categories of AEs are shown in Table 12.1-1. The definitions for each of these categories are given in the subsequent sections.

Table 12.1-1: Categories of Adverse Events

	NOT DEVICE- RELATED	DEVICE- OR PROCEDURE-RELATED	
NON- SERIOUS	Adverse Event (AE)	Adverse Dev (ADI	
	Serious Adverse	SERIOUS ADVERSE DEVICE EFFECT (SADE) (SEE 12.1.3)	
SERIOUS	EVENT	ANTICIPATED	UNANTICIPATED
	(SAE)	ANTICIPATED SERIOUS ADVERSE DEVICE EFFECT	UNANTICIPATED SERIOUS ADVERSE DEVICE EFFECT

CONFIDENTIAL AND PROPRIETARY

Study Protocol	Smith-Nephew
A Prospective, Multi-center, Randomized Controlled	Number:
Study to Evaluate the Safety and Efficacy of ARCR	REGENETEN.2020.01
augmented with REGENETEN™ Bioinductive Implant	Version: 2.0, 08 Dec
System in Full-thickness Tears (large or massive) Repair	2021
versus ARCR alone	Page: 76 of 134

(ASADE)	(USADE)
---------	---------

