12.1.2 Adverse Device Effect

An Adverse Device Effect (ADE) is an adverse event that is related to the use of the IP.

Note 1: This definition includes adverse events resulting from insufficient or inadequate instructions for use, deployment, implantation, installation or operation, or any malfunction of the investigational medical device.

Note 2: This definition includes any event resulting from use error or from intentional misuse of the investigational medical device.

CONFIDENTIAL AND PROPRIETARY

Study Protocol	Smith-Nephew
A Prospective, Multi-center, Randomized Controlled	Number:
Study to Evaluate the Safety and Efficacy of ARCR	REGENETEN.2020.01
augmented with REGENETEN™ Bioinductive Implant	Version: 2.0, 08 Dec
System in Full-thickness Tears (large or massive) Repair	2021
versus ARCR alone	Page: 77 of 134

Note 3: This includes comparator or if the comparator is a medical device.

- Not Related An AE is considered to be not related to the use of an IP or the procedure when the effect is DEFINITELY UNRELATED to have any relationship to the use of the IP or the procedure;
- Related An AE is considered to be related to the use of an IP or the procedure when there is a POSSIBLE, or DEFINITE relationship between the AE and the use of the IP or the procedure.

An ADE is further categorized depending on whether the criteria in section 12.1.3 and 12.1.4 are met.

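### Table 12.1-1 and section 12.1.2 disagree on whether an event due to the repair alone is an adverse device effect, so ADE and SADE counts could include repair complications

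*Combined protocol and SAP*

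**What the plan says.** Table 12.1-1 (section 12.1) has two columns. AE and SAE stand under "NOT DEVICE- RELATED". ADE and SADE, the latter split into anticipated and unanticipated, stand under "DEVICE- OR PROCEDURE-RELATED". The text above the table adds: "The definitions for each of these categories are given in the subsequent sections".

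The definition in section 12.1.2 does not mention the procedure: "An Adverse Device Effect (ADE) is an adverse event that is related to the use of the IP". Note 1 there extends it to events arising from, among other things, implantation of the device. Note 3 deals with the comparator in a sentence that cannot be parsed: "This includes comparator or if the comparator is a medical device". The same section then gives one relatedness rule for both causes: "An AE is considered to be related to the use of an IP or the procedure when there is a POSSIBLE, or DEFINITE relationship".

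Section 12.3 asks the investigator to judge each event against the device and against the procedure. Section 10.5 uses the labels as outputs: "adverse device effects, serious adverse device effects, and unanticipated serious device effects will be summarized". It also plans, for each adverse event, a summary of relationship to device use, and leaves any further safety summaries to the SAP. All of this is done in the safety set, which section 10.2 restricts to recipients of the study device.

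**The concern.** Every randomised subject has an arthroscopic cuff repair, and only one arm also receives the implant (section 8.1). The safety question specific to the device is what the implant adds to the repair. Section 4.4.4 lists complications of the surgery itself, such as infection, nerve or vessel injury, lasting pain or stiffness, and failure of the repair. A possible relationship is enough to count as related, so many such events could be judged procedure-related.

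If those events carry the ADE or SADE label, the headline device-safety counts mix two sources. If some sites follow the table and others the definition, the counts also depend on which paragraph a site read, across up to 30 sites. The label has further effects. Section 12.1.4 builds USADE on the serious ADE, so a serious event due only to the repair could be moved into or out of that class. Section 12.3 attaches product details to ADEs. Section 8.1 says the trial is to support registration in China and post-market follow-up elsewhere, where these counts would be read as properties of the device.

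**Working it through.** This is a question of definitions. The plan states no figure to reproduce and no arithmetic applies. The check is to pass each possible kind of event through each rule.

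**Inputs.** Table 12.1-1; the definition sentence, Note 1 and relatedness rule in section 12.1.2; the causality assessment in section 12.3; the outputs in section 10.5; the safety set in section 10.2.

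**Step 1: are the two table columns complementary?** The left column is *not device*. The right column is *device or procedure*. The complement of *device or procedure* is *neither device nor procedure*, which is narrower than *not device*. The columns therefore overlap in one cell: related to the procedure and not related to the device.

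**Step 2: classify the three kinds of event.**

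- Related to neither: left column only; AE or SAE by the definition. Unique.
- Related to the implant or its implantation: right column only; ADE or SADE by the definition and Note 1. Unique.
- Related to the repair, not to the implant: both columns of the table; AE or SAE by the definition sentence; simply related by the joint rule, with no split between device and procedure. Not unique.

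The conflict is confined to the third kind of event.

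**Step 3: does another section settle it?** Section 12.1.1 says adverse events include those related to procedures, but it also uses AE as the umbrella term, so it does not decide. Section 12.3 names device and procedure as two things to evaluate. Sections 12.5.1 and 9.1.11.1.2 also name the two separately. These show that the protocol can distinguish the concepts, but none says whether the table or the definition sentence determines the label.

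**Step 4: follow the label into the outputs.** Section 10.5 counts subjects with ADEs, SADEs and unanticipated serious effects.

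- If the table is applied, the third kind of event enters those counts.
- If the definition sentence is applied, it does not.
- The separate summary of relationship to device use would show how many events were judged device-related. It would identify the repair-only events only if that judgement is recorded apart from the procedure judgement. Section 12.3 requires both evaluations; the documents do not show two eCRF fields.

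**Step 5: look for a comparator.** A repair-only event should arise in both arms, so the ARCR-alone frequency would show the background. Section 10.5 uses the safety set for all safety endpoints, and section 10.2 limits that set to device recipients. Read literally, no ARCR-alone count is produced.

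**The case against.** The strongest reply is that the table is only an overview. Its own introduction sends the reader to the sections that follow for the definitions, and the definition there is tied to the product. On that reading a repair-only event is an AE or SAE and the counts are clean. This is a fair reading, and for that reason the effect is conditional. It does not remove the conflict: the table heading is explicit, the relatedness rule a few lines below the definition brings the procedure back in, and no precedence is stated.

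A second reply is that *procedure* may mean placing the implant. Section 6.5 uses the word in that sense, and Note 1 already counts implantation events as ADEs. That would narrow the conflict, but the protocol does not define the term, and section 4.4.4 describes risks of the surgery as a whole.

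Several stronger readings are tempting and are not supported:

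- A reader might infer that the counts *will* absorb repair complications. That follows only if the table is applied.
- A reader might take the joint rule itself to label procedure-related events as ADEs. It sets the threshold for calling an event related; only the table heading supplies the label.
- A reader might expect ADEs to be tabulated for ARCR-alone subjects without an implant. The safety set as written leaves those subjects out, so the problem for the tables is the lack of a comparator. Note 3 also leaves unclear whether comparator events can be ADEs at all.
- A reader might conclude that device-attributed events cannot be seen at all. The summary of relationship to device use gives some view of them, and the SAP may add more.

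**Conclusion.** The inconsistency is real and limited. One class of event, related to the repair and not to the implant, has no unique category, and it feeds directly into counts that section 10.5 plans to report. If the table is applied, ADE, SADE and USADE counts could include complications of the repair, with no ARCR-alone figure in the safety set to put them in context. The device-relationship summary is a partial offset.

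The size cannot be stated, because the documents give no rates for repair-related or implant-related events. A reader might try to size it from the 15% retear incidence assumed for the device arm in section 11, which is 0.15 × 130 = 19.5 subjects. That is an efficacy planning assumption. The documents do not say that retears are recorded as adverse events or judged procedure-related, so it does not measure this effect.

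The conclusion rests on two readings: that *procedure* includes the cuff repair, and that the safety set means what section 10.2 says. It should be settled before database lock.

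**What to change.** 1. **Section 12.1.** Reconcile Table 12.1-1 with section 12.1.2. Head the right column as device-related, with the existing left heading as its true complement, so that ADE, SADE and USADE depend on relationship to the device. Keep events from implantation as ADEs, as in Note 1. Rewrite Note 3 so that the status of comparator events is clear.
2. **Section 12.1.2.** State the relatedness rule twice, once for the device and once for the procedure, and say what *procedure* covers.
3. **eCRF.** Confirm that the two assessments required by section 12.3 are held in separate fields.
4. **Sections 10.2 and 10.5.** Define a safety set that includes ARCR-alone subjects. Tabulate procedure-related adverse events by arm in all treated subjects, separately from ADEs.

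Items 1 and 2 cost wording only. Item 3 costs a check; if there is a single field, it costs an added field and a review of events already entered. Item 4 is the larger change, since it alters an analysis set and adds a table. Section 12.3 sets the same reporting time for SAEs and SADEs, so relabelling a serious event does not change that time. Nothing here changes treatment or visits.

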12.1.1 Adverse Event

An Adverse Event is any untoward medical occurrence, unintended disease or untoward clinical sign (including abnormal laboratory findings) in subjects, users or other persons, whether or not causally related to the IP and whether anticipated or unanticipated.

- Note 1: This definition includes events related to the IP, comparator or ancillary products.
- Note 2: This definition includes events related to the procedures involved.
- Note 3: For users or other persons, this definition is restricted to events related to the IP

AE is used both to refer to AE which do not meet the definitions of Adverse Device Effects or Serious Adverse Events and as an umbrella term referring to adverse events of all classifications.

An AE can be any unfavorable and unintended sign (for example, an abnormal laboratory finding), symptom, or disease. For reporting purposes, emphasis is placed first and foremost on whether or not the event constitutes an untoward medical occurrence.

12.1.2 Adverse Device Effect

An Adverse Device Effect (ADE) is an adverse event that is related to the use of the IP.

Note 1: This definition includes adverse events resulting from insufficient or inadequate instructions for use, deployment, implantation, installation or operation, or any malfunction of the investigational medical device.

Note 2: This definition includes any event resulting from use error or from intentional misuse of the investigational medical device.

CONFIDENTIAL AND PROPRIETARY

Study Protocol	Smith-Nephew
A Prospective, Multi-center, Randomized Controlled	Number:
Study to Evaluate the Safety and Efficacy of ARCR	REGENETEN.2020.01
augmented with REGENETEN™ Bioinductive Implant	Version: 2.0, 08 Dec
System in Full-thickness Tears (large or massive) Repair	2021
versus ARCR alone	Page: 77 of 134

Note 3: This includes comparator or if the comparator is a medical device.

- Not Related An AE is considered to be not related to the use of an IP or the procedure when the effect is DEFINITELY UNRELATED to have any relationship to the use of the IP or the procedure;
- Related An AE is considered to be related to the use of an IP or the procedure when there is a POSSIBLE, or DEFINITE relationship between the AE and the use of the IP or the procedure.

An ADE is further categorized depending on whether the criteria in section 12.1.3 and 12.1.4 are met.

12.1.3 Serious Adverse Events and Serious Adverse Device Effects

An AE or ADE is considered a **Serious** Adverse Event (SAE) or **Serious** Adverse Device Effect (SADE) if, in the view of either the Investigator or the Sponsor, it led to any of the following:

- a) death,
- b) serious deterioration in the health of the subject, users or other persons as defined by one or more of the following:
 - 1) a life-threatening illness or injury, or
 - 2) a permanent impairment of a body structure or a body function including chronic disease, or
 - 3) in-patient or prolonged hospitalization, or
 - 4) medical or surgical intervention to prevent life-threatening illness or injury or permanent impairment to a body structure or a body function,
- c) foetal distress, foetal death or a congenital abnormality or birth defect including physical or mental impairment.

CONFIDENTIAL AND PROPRIETARY

Study Protocol	Smith-Nephew
A Prospective, Multi-center, Randomized Controlled	Number:
Study to Evaluate the Safety and Efficacy of ARCR	REGENETEN.2020.01
augmented with REGENETEN™ Bioinductive Implant	Version: 2.0, 08 Dec
	2021
versus ARCR alone	Page: 78 of 134

Note: Planned hospitalization for a pre-existing condition, or a procedure required by the study protocol, without serious deterioration in health, is not considered a serious adverse event.

12.1.4 Anticipated/Unanticipated Serious Adverse Device Effect

An Unanticipated Serious Adverse Device Effect (USADE) is a serious ADE which by its nature, incidence, severity or outcome has not been identified in the current version of the risk analysis report.

Guidance Regarding the Determination of Unanticipated Events:

During causality assessment activity, clinical judgement shall be used and the relevant documents, such as the Investigator's Brochure, the Clinical Protocol or the Risk Analysis Report shall be consulted, as all the foreseeable serious adverse events and the potential risks are listed and assessed there. The presence of confounding factors, such as concomitant medication/treatment, the natural history of the underlying disease, other concurrent illness or risk factors shall also be considered. [MEDDEV 2.7/3 Rev 3 Sec 8].

Note: An anticipated serious adverse device effect (ASADE) is an effect which by its nature, incidence, severity or outcome has been identified in the risk analysis report (see Section 4.4 for details).

12.1.5 Severity

The severity of every AE will be assessed by the PI or medically qualified site staff to whom the responsibility has been delegated and documented on the delegation of authority log. AE should be classified as mild, moderate, or severe, regardless of whether or not the AE are considered to be serious or non-serious. The classification should be based on the following definitions:

Mild - An event is mild if the subject is aware of, but can easily tolerate the sign or symptom;

CONFIDENTIAL AND PROPRIETARY

Study Protocol	Smith-Nephew
A Prospective, Multi-center, Randomized Controlled	Number:
Study to Evaluate the Safety and Efficacy of ARCR	REGENETEN.2020.01
augmented with REGENETEN™ Bioinductive Implant	Version: 2.0, 08 Dec
System in Full-thickness Tears (large or massive) Repair	2021
versus ARCR alone	Page: 79 of 134

- **Moderate** An event is moderate if the sign or symptom results in discomfort significant enough to cause interference with the subject's usual activities;
- **Severe** An event is severe if the sign or symptom is incapacitating and results in the subject's inability to work or engage in their usual activities.

12.1.6 Device Deficiency

A Device Deficiency (DD) is an inadequacy of a medical device with respect to its identity, quality, durability, reliability, safety or performance.

Note: DD includes malfunctions, use errors and inadequacy in the information supplied by the manufacturer including labelling.

Device deficiencies that did not lead to an adverse event but could have led to a medical occurrence

- a. if either suitable action had not been taken,
- b. if intervention had not been made, or
- c. if circumstances had been less fortunate,

are considered Device Deficiencies with potential to cause SADE and shall be reported as specified in section 12.3.

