12.3 Reporting Procedures

AE of any kind and DD will be recorded in the applicable eCRF and source notes. The Investigator will evaluate all AE for relationship to the device and procedure, seriousness, and severity. DD will be evaluated for potential to cause SADE. The following timescales should be followed for the AE/DD information to be entered into the eCRF and reported to the Sponsor or designee (see Figure 12.3-1 and Figure 12.3-2):

- ADE and DD without unreasonable delay
- SAE, SADE and DD with potential to cause SADE immediately (i.e. within 24 hours of the investigator being informed about the event)

For ADE and DD, details of the product/procedure related to the event will be included and where applicable, pictures taken of the device. The deficient product should be retained for return to Smith+Nephew unless it is contaminated (e.g., used dressings must not be retained). Updates to submitted information will be recorded in the eCRF according to the timescales above.

All adverse events will be reviewed by a medically qualified person appointed by the Sponsor to determine which, if any, meet criteria for expedited reporting to the regulatory authorities.

[figure not shown]
The investigator will inform the IRB/EC of adverse events according to the IRB/EC requirements.

Depending on the nature of the adverse event, Smith+Nephew may request copies of the subject's medical records, Imaging, Operative notes, as well as results of any relevant laboratory tests performed or other documentation related to the AE. If the subject was hospitalized, a copy of the discharge summary may be requested by Smith+Nephew and should be forwarded as soon as it becomes available. In certain cases, Smith+Nephew also may request a letter from the Investigator that summarizes the events related to the case. Refer to the ISF Sponsor Contact Information Sheet to report SAE, unanticipated SADE, anticipated SADE, and DD.

CONFIDENTIAL AND PROPRIETARY

[figure not shown]
Study Protocol	Smith-Nephew
A Prospective, Multi-center, Randomized Controlled	Number:
Study to Evaluate the Safety and Efficacy of ARCR	REGENETEN.2020.01
augmented with REGENETEN™ Bioinductive Implant	Version: 2.0, 08 Dec
System in Full-thickness Tears (large or massive) Repair	2021
	Page: 81 of 134

Figure 12.3-1: Evaluation and Reporting of Adverse Events

Study Protocol	Smith-Nephew
A Prospective, Multi-center, Randomized Controlled	Number: REGENETEN.2020.01

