System in Full-thickness Tears (large or massive) Repair	2021
	Page: 130 of 134

- emergency treatment, including decoding procedures for blinded/masked clinical investigations, as needed,
- f. ensure that clinical records are clearly marked to indicate that the subject is enrolled in a particular clinical investigation,
- g. if appropriate, subjects enrolled in the clinical investigation shall be provided with some means of showing their participation in the clinical investigation, together with identification and compliance information for concomitant treatment measures (contact address and telephone numbers shall be provided),
- h. inform, with the subject's approval or when required by national regulations, the subject's personal physician about the subject's participation in the clinical investigation, and
- make all reasonable efforts to ascertain the reason(s) for a subject's premature withdrawal from the clinical investigation while fully respecting the subject's rights.
- 8. Safety reporting. The Principal Investigator shall:
 - record every adverse event and observed device deficiency, together with an assessment,
 - report to the Sponsor, without unjustified delay, all serious adverse events and device deficiencies that could have led to a serious adverse device effect; this information shall be promptly followed by detailed written reports, as specified in the protocol,
 - c) report to the IEC serious adverse events and device deficiencies that could have led
 to a serious adverse device effect, if required by the national regulations or protocol or
 by the IEC,
 - d. report to regulatory authorities serious adverse events and device deficiencies that could have led to a serious adverse device effect, as required by the national regulations, and
 - e. supply the Sponsor, upon Sponsor's request, with any additional information related to the safety reporting of a particular event.

Study Protocol	Smith-Nephew
A Prospective, Multi-center, Randomized Controlled	Number:
Study to Evaluate the Safety and Efficacy of ARCR	REGENETEN.2020.01
augmented with REGENETEN™ Bioinductive Implant	Version: 2.0, 08 Dec
System in Full-thickness Tears (large or massive) Repair	2021
versus ARCR alone	Page: 131 of 134

21.6 RESPONSIBILITIES OF CLINICAL TRIAL INSTITUTION AND INVESTIGATOR (CFDA CHINA FOOD AND DRUG ADMINISTRATION)

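### Section 12.1.6 defines a device deficiency with potential to cause a SADE without requiring seriousness and only where no adverse event occurred, in conflict with Appendix 21.5 item 8

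*Combined protocol and SAP*

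**What the plan says.** Section 12.1.6 starts from "Device deficiencies that did not lead to an adverse event but could have led to a medical occurrence", adds three alternative conditions (a) to (c) (no suitable action, no intervention, less fortunate circumstances), and concludes that such deficiencies "are considered Device Deficiencies with potential to cause SADE and shall be reported as specified in section 12.3".

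Section 12.3 sets two reporting speeds to the sponsor or its designee. The slower is "ADE and DD without unreasonable delay". The faster is "SAE, SADE and DD with potential to cause SADE immediately (i.e. within 24 hours of the investigator being informed about the event". The same section says that "DD will be evaluated for potential to cause SADE", without restricting this to deficiencies with no AE, and that "All adverse events will be reviewed by a medically qualified person appointed by the Sponsor".

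Section 10.5 counts all device deficiencies and the patients who report one, and adds a "summary of device deficiencies with the potential to cause SADE".

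Appendix 21.5 item 8 obliges the principal investigator to report "device deficiencies that could have led to a serious adverse device effect". It sets no number of hours. Section 13 binds principal investigators to the requirements in Appendix 21.5.

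**The concern.** The class is named for serious effects, yet its definition has no seriousness test. It also shuts out every deficiency that led to an AE, however mild, although some actual harm with worse narrowly avoided is informative about device safety. Appendix 21.5 item 8 has the seriousness test and lacks the no-AE limit, so investigators work under two different tests for one class.

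The label has two uses. It puts a deficiency on the 24-hour route to the sponsor, and it decides what is counted in one of the section 10.5 summaries. With up to 30 sites, two tests invite inconsistent classification, and the summary then depends on which text a site followed.

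**Working it through.** No arithmetic applies, and the plan states no figure to reproduce. The check applies the two texts to each kind of deficiency.

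Inputs:
- Section 12.1.6: in the class if no AE occurred and some medical occurrence was possible under (a), (b) or (c).
- Appendix 21.5 item 8: in the class if a SADE was possible. It is silent on whether an AE occurred.
- Section 12.1.1: an AE is any untoward medical occurrence, so a mild sign is enough.
- Section 12.1.3: an event is serious according to what it led to, not what it might have led to.
- Section 12.3: 24 hours for SAEs, SADEs and potential-SADE deficiencies; no fixed hours for other adverse device effects (ADE) and DDs.

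| Case | What happened | Worst that could have followed | Class under 12.1.6 | Class under 21.5 item 8 |
|---|---|---|---|---|
| 1 | No AE | Nothing medical | Out | Out |
| 2 | No AE | A non-serious occurrence only | In | Out |
| 3 | No AE | A serious device effect | In | In |
| 4 | Non-serious AE | Nothing serious | Out | Out |
| 5 | Non-serious AE | A serious device effect | Out | In |

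A deficiency that actually caused a SADE is on the 24-hour route under either text, so it is left out of the table.

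The texts agree in cases 1, 3 and 4 and disagree in cases 2 and 5.

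- Case 2 is over-inclusion. Under 12.1.6 it gets the 24-hour report and enters the 10.5 summary, although no serious effect was possible.
- Case 5 is under-inclusion. It fails 12.1.6 because an AE occurred, and it is not a SADE under 12.1.3 because nothing serious resulted. It is recorded as an ADE and a DD and goes by the slower route. Between cases 3 and 5 the potential for serious harm is the same, but the case with actual minor harm has the less urgent route.

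The general evaluation sentence in 12.3 does not clearly settle case 5. It covers all deficiencies, and a SADE is defined with seriousness in 12.1.3, so it can be read the way 21.5 reads. But the only definition of the potential-SADE class in section 12 is the one in 12.1.6, so a site can equally read the sentence as pointing back to it. Review of the AE by the sponsor's medically qualified person does not by itself relabel the deficiency.

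**The case against.** A reader might infer that case 5 is missed altogether. The documents do not support that. It is recorded and reported as both an ADE and a DD, its AE is medically reviewed for the sponsor, the 12.3 evaluation covers every deficiency, and Appendix 21.5 reaches it through section 13. In China, Article 72 in Appendix 21.6 also requires all adverse events and device defects to be recorded and analysed with the sponsor. Some apparent examples are not case 5 at all: under 12.1.3, an event needing intervention to prevent life-threatening injury or permanent impairment is already serious and takes the 24-hour route.

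Nor are all trivial deficiencies swept in. Case 1 stays out, and the extra cases in case 2 err in the cautious direction. The faster route is only a report to the sponsor; expedited reporting to authorities depends on the sponsor's medical review.

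The 24-hour limit comes from 12.3 alone. Appendix 21.5 asks only for reporting without unjustified delay, so the conflict with the appendix concerns who belongs in the class, not speed.

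The content of Figure 12.3-2, on evaluating and reporting device deficiencies, was not available for this check. It may state a rule. If that rule follows 21.5, it conflicts with 12.1.6; if it follows 12.1.6, the problem is repeated there.

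These points limit the consequences. They leave the conflict between 12.1.6 and 21.5 item 8 in place.

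**Conclusion.** The inconsistency is real and lies in the current text. Read literally, 12.1.6 misplaces two kinds of deficiency: those able to cause only a non-serious occurrence are put in the class, and those that caused a non-serious AE but could have caused a serious effect are left out. The second kind loses the 24-hour route and assured inclusion in the 10.5 summary, and nothing more.

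The effect is confined to reporting speed and one descriptive sub-count. The counts of all deficiencies, of patients with a deficiency and of ADEs in section 10.5 do not depend on the label. The primary endpoint, power and error rates are unaffected.

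Two further inferences should be resisted. One is a numerical estimate of misclassified deficiencies: the documents give no deficiency rate and no split by potential seriousness, so any figure would rest wholly on assumption. The other is that this sub-count forms part of the Chinese registration safety data: the synopsis and section 8.1 say the study supports registration there, but no section says so of this summary.

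The conclusion assumes that sites apply 12.1.6 as written and that Figure 12.3-2 does not override it.

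**What to change.** Reconcile 12.1.6 with 12.3 and Appendix 21.5 item 8 through three changes to the definition:

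1. Require that the deficiency could have led to a serious adverse device effect, in place of any medical occurrence.
2. Keep conditions (a) to (c) as they stand in 12.1.6.
3. Remove the limit to deficiencies without an AE, and state that those with a non-serious AE are included.

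The result combines the two texts: the seriousness test comes from 21.5 item 8 and the conditions from 12.1.6. The explicit inclusion of deficiencies with a non-serious AE is new wording, since item 8 is silent on it. Use the same definition in 12.3, Figure 12.3-2 and the 10.5 summary.

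The cost is one definition and one reclassification of deficiencies already recorded. No patients, visits or assessments are added.
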